Methods: Adult patients presenting for endoscopic closure of a gastrointestinal luminal defect will be enrolled and randomized 1:1 to closure of the defect with either the X-Tack system (the study group) or the Overstitch system (the control group.) Demographics, comorbidities, laboratory values, size of defect, time to close the defect, and the number of sutures to close the defect will be recorded. The primary outcome will be the time to closure of the defect. Secondary outcomes will include the rate of incomplete closures (as defined as either crossover to the other study group per endoscopist's discretion, or the need for additional modalities to close the defect such as endoscopic clips) as well as complications (bleeding, infection, perforation) and costs. Time to closure will be compared using the student T-test. To detect a 5-minute mean difference between the two groups at 80% power with an alpha of 0.05 and 1:1 randomization, 16 patients will be required in each group. Anticipating loss of subjects or data for technical or unanticipated reasons after randomization, we expect that 50 patients will need to be enrolled.

A. Specific Aims

The primary objective of the study is to compare the time required to close a defect or fistula in the gastrointestinal tract between the X-Tack system and the current standard of care (suturing with the Overstitch system.) The secondary objectives of the study will be to compare the rate of incomplete closures (as defined as either crossover to the other

study group per endoscopist's discretion, or the need for additional modalities to close the defect such as endoscopic clips) as well as complications (bleeding, infection, perforation) and costs between the X-Tack system and the current standard of care. We hypothesize that the X-Tack system will permit faster closure of endoscopic defects compared to the current standard, because the X-Tack does not require a different endoscope to use.

B. Background and Significance

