Perforation rates with endoscopic submucosal dissection (ESD) of colonic lesions and early cancers can be as high as 4% with delayed bleeding rates up to 8%. Endoscopic closure of resection defects has been shown to reduce delayed bleeding rates in the colon and is the least invasive method for closure of perforations or fistulas. Current options for closure include through-the-scope (TTS) clips, over-the-scope clips (OTSC,) and endoscopic suturing with the Overstitch system. TTS clips frequently misdeploy or are dislodged during complex closures and are cumbersome for the closure of large defects. OTSC are limited to closure of ~2 cm defects but are unable to capture the entirety of larger defects. The Overstitch system can close defects of any size but requires the use of a double-channel endoscope that is wide in diameter and is often too short to reach the right colon. It also requires removal of the endoscope that is being used for the resection from the patient in order to introduce the double-channel scope for closure. The X-Tack system offers the ability to close large defects with endoscopic sutures but can be introduced through the instrument channel of any standard endoscope, filling the gap between clips and suturing.

[figure not shown]
C. Preliminary Studies/Progress Report

The X-Tack is currently FDA cleared on the basis of similarity to previous suturing devices, though human data is pending. Preclinical animal data primarily compared the X-Tack to through-the-scope (TTS) clips. In the 24 X-Tack cases, 21 could be closed with just one X-Tack device, while a second device was used in 3 cases. Technical closure of defects in the animal model was successful in 24/24 cases using the X-Tack, versus just 13/16 cases using TTS clips. On necropsy, the time to complete healing of the defects was comparable between the X-Tack and TTS clip cases. On this basis, the investigators concluded that the X-Tack achieved expected levels of tissue healing and higher technical success rates than the current standard of care.

D. Research Design and Methods

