Time to closure will be compared using the student T-test. To detect a 5-minute mean difference between the two groups at 80% power with an alpha of 0.05 and 1:1 randomization, 16 patients will be required in each group (32 patients in total.) Anticipating loss to follow-up and patient dropout, we expect that a total of 50 patients will be required. Categorical variables will be compared using the chi squared test.

F. Gender/Minority/Pediatric Inclusion for Research

Women and minorities will be included in the research protocol.

G. Human Subjects

1. Provide number, age range, and health status of the subject population. List criteria for inclusion or exclusion.

We anticipate enrolling 50 patients in total.

Inclusion criteria: Patients > 18 years of age undergoing closure of a gastrointestinal luminal defect for which a suturing device would be otherwise indicated.

Exclusion criteria: INR > 2, platelets < 150, ongoing anticoagulation not meeting ASGE Antithrombotic Guidelines (Acosta RD et al, The Management of Antithrombotic Agents for Patients Undergoing GI Endoscopy, Gastrointest Endosc, 2016; 83(1): 3-16,) hemodynamic instability, ongoing or anticipated pregnancy

2. Identify sources of research material in the form of specimens, records or data.

Records and data will include chart data including demographics and comorbidities, laboratory values, endoscopy reports, and video acquired during endoscopy.

3. Describe plans for recruitment and consent procedures to be followed.

The endoscopist performing the procedure will meet the potential subject in the pre-procedure holding area. The endoscopist will review the consent documents with the potential subject. The subject will be provided time to review the entirety of the document and ask any questions of the endoscopist that they have. If they are amenable to proceeding, they will sign the consent and the procedure will be performed. No additional recruitment or inducement (i.e. advertising) is anticipated.

4. Describe risks and assess likelihood and seriousness.

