The primary potential risk of this research is device failure (i.e. failure to close defect or complications of closure, such as bleeding or perforation.) Device failure is expected to be uncommon. Most device failures are expected to be minor (i.e. perhaps requiring an additional device to complete closure of the rest of the defect, but no immediate harms or risks to the patient besides longer procedure time.) Serious complications (i.e. bleeding or perforation attributable to the device and requiring hospitalization) are expected to be very rare.

5. Describe procedures for protecting against or minimizing potential risks.

Because the research device will be used for defect closure during the same period of sedation as the current standard of care, participants should not perceive any difference in their procedure beyond signing an additional consent form. Patients with a propensity for bleeding i.e. thrombocytopenia or coagulopathy will be excluded to avoid adverse events.

6. Describe potential benefits and importance to the subjects and others.

Participants could potentially benefit from a faster defect closure with reduced anesthesia time. The ease of deployment of the X-Tack device also might make clinical success more likely. If the X-Tack device proves to be a faster, safer way to close mucosal defects or fistulas, future patients undergoing endoscopic submucosal dissection or fistula closure could benefit from less anesthesia time and a better chance at clinical and technical success.

7. Discuss why risks are reasonable in relation to benefits.

The risks and side effects of closure with the X-Tack system are anticipated to be identical to those of the Overstitch system. Given that the Overstitch is the current standard of care, and the X-Tack is anticipated to be faster and more user-friendly, the benefits of introducing the X-Tack outweigh the risks.

H. Data and Safety Monitoring Plan

1. Data and Safety Monitoring Plan (DSMP)

a. reporting mechanisms for adverse events to the IRB, FDA, and NIH.

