Adverse events will be tracked and reported to the IRB at the time of interim analysis and final analysis (anticipated study time is less than one year.) Adverse events will be defined as bleeding, infection, or perforation occurring within 72 hours of the procedure. Severe adverse events will be reported to the IRB at the time of occurrence. Adverse events will be defined using the ASGE Adverse Event Lexicon (Cotton PB et al, A lexicon for endoscopic adverse events: report of an ASGE workshop. *Gastrointest Endosc*, 2010; 71(3): 446-454.) Severe adverse events in this lexicon are considered any adverse events resulting in hospital admission >10 days, ICU admission > 1 night, surgery for an adverse event or permanent disability. Severe adverse events will be reported using the OHR online portal.

b. adverse event (AE) grading

Adverse events will be graded according to the ASGE adverse event lexicon.

c. plan for unanticipated AE reporting

Severe adverse events will be reported to the IRB at the time of occurrence.

d. plan for annual reporting of AEs

The anticipated study time is less than one year, thus all reporting will occur at the time of interim analysis and final analysis.

e. interim efficacy analysis where appropriate

Perforation rate and complications related to inadequate closure (leak, fistula, peritonitis, bleeding) will be monitored. Perforation or complications related to inadequate closure > 50% compared to control group will lead to

stoppage of the trial. Interim analysis will be performed at the midpoint of enrollment (25 patients.) For instance, if after 25 patients have enrolled, 2 patients in the control group experience a complication, yet 4 experience a complication in the X-Tack group, the results will be reviewed with the independent safety monitor for possible stoppage of the trial pending discussion with the IRB.

2. If applicable, describe the Data and Safety Monitoring Board (DSMB) that will be responsible for monitoring the study.

An independent reviewer has been selected within the Jefferson Division of Gastroenterology who is outside of the investigator group who will review the interim analysis.

I. Literature Cited

2. Pohl H, et al. Clip Closure Prevents Bleeding After Endoscopic Resection of Large Colon Polyps in a Randomized Trial. *Gastroenterology* 2018;157:977-984.

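### The threshold of a more than 50% excess over control, read at 12-13 patients per arm with no allowance for chance, can support a trigger for review but not a mandatory stop

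*Combined protocol and SAP*

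**What the plan says.** Section H.1.e monitors perforation and complications of inadequate closure (leak, fistula, peritonitis, bleeding). Its rule is "Perforation or complications related to inadequate closure > 50% compared to control group will lead to" stoppage of the trial. The timing is "Interim analysis will be performed at the midpoint of enrollment (25 patients"), which is half of the total in section G.1: "We anticipate enrolling 50 patients in total". The Methods summary says patients are "enrolled and randomized 1:1 to closure of the defect".

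The same paragraph then gives an example at 25 patients: "2 patients in the control group experience a complication, yet 4 experience a complication in the X-Tack group". The consequence there is softer: "the results will be reviewed with the independent safety monitor for possible stoppage of the trial pending discussion with the IRB".

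Two other places bear on the size of the problem. Section G.7 says the risks of X-Tack "are anticipated to be identical to those of the Overstitch system". Section B says that perforation rates after colonic submucosal dissection "can be as high as 4% with delayed bleeding rates up to 8"%. No section gives an expected rate for the composite that H.1.e monitors.

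**The concern.** The threshold is a bare relative excess. It has no minimum number of events, no interval or test, and no convention for a control arm with no events. With 12 or 13 patients per arm, complication counts will be small and their ratio will move sharply with each event. A number that is often exceeded by chance is a weak basis for a sentence that says the trial will stop.

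Two things are at stake. Read literally, the rule could end a 50-patient comparison at its midpoint on one event. Read as the example reads it, the independent reviewer is handed an excess with nothing in the plan to show how often chance alone would produce it.

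**Working it through.** **The plan's own figures.** 50/2 = 25 patients, which under 1:1 allocation is 12 and 13. In the example, 4 v 2 is 100% more by count. By rate it is (4/12)/(2/13) − 1 = +117%, or (4/13)/(2/12) − 1 = +85%. It exceeds 50% either way. The absolute gap is 18 or 14 percentage points, so the example fits only a relative reading of 50%.

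**What counts meet the threshold.** With x events among n_T X-Tack patients and y among n_C controls, it is met when x/n_T > 1.5 × y/n_C. The smallest X-Tack count that meets it is:

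| Control events | X-Tack 12, control 13 | X-Tack 13, control 12 |
|---|---|---|
| 0 | 1 | 1 |
| 1 | 2 | 2 |
| 2 | 3 | 4 |
| 3 | 5 | 5 |

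So 1 v 0 and 2 v 1 are enough. At 3 v 2 the answer depends on which arm has the 13th patient: (3/12)/(2/13) − 1 = +62%, but (3/13)/(2/12) − 1 = +38%. By raw counts it is exactly +50%, which is not above 50%.

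**Strength of evidence at these counts (two-sided Fisher).** 2/12 v 1/13: p = 0.59. The example, 4 v 2: p = 0.38 (4/12 v 2/13) or 0.64 (4/13 v 2/12).

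**Chance of meeting the threshold.** For true rates p_T and p_C, add Bin(x; n_T, p_T) × Bin(y; n_C, p_C) over all tables that meet it. As an illustration with equal rates of 8% and a 12/13 split:

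- y = 0 and x ≥ 1: 0.3383 × 0.6323 = 0.2139
- y = 1 and x ≥ 2: 0.3824 × 0.2487 = 0.0951
- y = 2 and x ≥ 3: 0.1995 × 0.0652 = 0.0130
- y = 3 and x ≥ 5: 0.0001

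The total is 0.322. Without the first line (no control events) it is 0.108.

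The true rate is an assumption. The range below spans low rates, section B's two upper values (4% and 8%), their sum (12%), and a rate above the example's control rate of about 16%. Ranges are over the 12/13 and 13/12 splits.

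| Control rate (assumed) | Equal risk, threshold met | Equal risk, met with at least one control event | True doubling, threshold met |
|---|---|---|---|
| 1% | 10-11% | 0.1% | 19-21% |
| 2% | 17-19% | 0.5% | 31-34% |
| 4% | 25-28% | 3% | 46-49% |
| 8% | 32-35% | 11% | 59-60% |
| 12% | 34-36% | 19% | 64% |
| 20% | 32% | 25-27% | 68-69% |

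The plan does not say whether allocation is blocked. Under simple randomization of 25 patients the equal-risk figures are 27% at 4%, 34% at 8% and 35% at 12%, so the split is not what drives the result.

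**How often one event decides it.** With a 12/13 split and equal risk, removing a single X-Tack event would undo 80% of the triggers at a 4% rate, 65% at 8% and 56% at 12%.

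**The case against.** The strongest reply is that the threshold does not by itself end the trial. The worked example is well above 50%, yet its consequence is review by the independent monitor and discussion with the IRB. For a device whose human data are still pending (section C), a sensitive trigger for a conversation is defensible, and a false alarm then costs only that conversation. This stands as far as the example goes. It does not remove the rule sentence, which names stoppage as the consequence.

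A reader might infer that about a third of trials of two identical devices would be stopped. The documents do not support that, for three reasons.

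- A third needs a composite complication rate of roughly 8-20%, and no such rate is given. Section B's figures are upper values for colonic dissection, and the same section says closure reduces delayed bleeding. Section G.4 expects serious complications to be very rare. At 1-2% the figure is 10-19%.
- It counts any X-Tack event against no control events as more than 50% higher. A relative excess over zero is undefined, and the plan does not say how to treat it. At low rates most triggers come from these tables: 0.228 of 0.254 at 4% with a 12/13 split.
- Meeting the threshold is not the same as stopping, given the example.

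A reader might also infer that the plan is wrong for lacking a formal stopping boundary, such as a posterior probability of at least 0.90. That is a trade-off, not a correction. With Jeffreys priors and a 12% control rate, such a boundary would flag a true doubling in only 31-34% of trials, against about 64% for the present threshold. Its cut-offs also depend on the split: against 0, 1, 2 and 3 control events it needs 2, 4, 5 and 6 X-Tack events with 12 v 13, but 2, 4, 6 and 7 with 13 v 12.

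**Conclusion.** The concern holds in this limited form: the threshold separates harm from chance too poorly to mandate stopping, although it is usable as a prompt for review. At an assumed rate of 4% it is met in 25-28% of trials when the devices are equally risky and 46-49% when X-Tack doubles the risk. At 12% the figures are 34-36% and about 64%.

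These results assume one look at 25 patients, a 12/13 or 13/12 split, independent events, a relative reading of 50%, and the literal reading in which any event against none meets the threshold. The largest uncertainties are the true composite rate and the zero-control convention, and the plan settles neither. The primary comparison of closure times is not affected. The change should be made before the interim look, but the point is not fatal to the design.

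**What to change.** In section H.1.e:

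1. Reconcile the rule sentence with the worked example, so that exceeding the threshold triggers review by the independent monitor and discussion with the IRB, and does not by itself stop the trial.
2. Define the comparison on rates per patient with closure attempted, not on counts, so that unequal arms are handled consistently.
3. State how zero control events are treated.
4. Print the false-trigger and detection probabilities for both the 12/13 and 13/12 splits over a stated range of complication rates, so that the reviewer can judge whether an observed excess is beyond chance.

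Any further strength-of-evidence cut-off for stopping is optional. It is for the monitor and IRB to set, because it buys fewer false alarms with less sensitivity to real harm.

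The cost is one paragraph and a small table. The review trigger keeps its present sensitivity, and no sample size or endpoint changes.

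### After the single look at patient 25, non-severe perforations and closure complications have no defined route to the stopping rule before the final analysis

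*Combined protocol and SAP*

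**What the plan says.** Section G.1 sets the size of the trial: "We anticipate enrolling 50 patients in total".

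Section H.1.e states what is watched: "Perforation rate and complications related to inadequate closure (leak, fistula, peritonitis, bleeding) will be monitored". It then gives a threshold: "Perforation or complications related to inadequate closure > 50% compared to control group will lead to" stoppage of the trial. Neither sentence says when or how often the comparison is made. The only schedule follows: "Interim analysis will be performed at the midpoint of enrollment (25 patients"). An illustration comes next, in which after 25 patients "2 patients in the control group experience a complication, yet 4 experience a complication in the X-Tack group". The stated response there is a review with the independent safety monitor about possible stoppage, subject to discussion with the IRB.

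Section H.2 names an independent reviewer within the division but outside the investigator group, "who will review the interim analysis". No other duty is stated.

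Sections H.1.a and H.1.d place routine adverse event reporting to the IRB at the interim and final analyses. The exception, in H.1.a and H.1.c, is: "Severe adverse events will be reported to the IRB at the time of occurrence". H.1.a defines severe as a hospital stay over 10 days, more than one night in intensive care, surgery for the event, or permanent disability.

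Section C says that X-Tack is FDA cleared on similarity to earlier suturing devices, "though human data is pending".

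**The concern.** The rule in H.1.e compares the arms, so someone must hold cumulative counts by arm to apply it. The plan provides for that at patient 25 and at the end. Half of the planned exposure falls in between.

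Take a bleed, leak or perforation in patient 30 that leads to a five-day admission. It does not meet the definition of severe. As written, it reaches the IRB with the final analysis, and no step sends it to the reviewer. A severe event does reach the IRB at once, but as a single report with no stated tally by arm.

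The one scheduled look has about 12 or 13 patients per arm. With so few, a real excess will often not have shown itself yet. The rule protects patients against inadequate closure by a device for which the protocol reports no human data. If an excess becomes visible at patient 35, the plan assigns nobody to see it.

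**Working it through.** **The plan's own figures.** The midpoint is 50/2 = 25, as stated. In the illustration the ratio of counts is 4/2 = 2.0. As rates it is (4/13)/(2/12) = 1.85 with 13 X-Tack v 12 control, or (4/12)/(2/13) = 2.17 with 12 v 13. Either exceeds 1.5, so the illustration agrees with the threshold if that is read as a relative excess above 50%.

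**Who sees what, and when.**

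| Information | Patients 1-25 | Patients 26-50 |
|---|---|---|
| Scheduled comparison by arm | at patient 25 | final analysis |
| Stated duty of independent reviewer | interim analysis | none stated |
| Non-severe events to the IRB | at the interim | final analysis |
| Severe events to the IRB | as they occur | as they occur, no stated tally by arm |

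**Inputs for the size.** From the documents: 50 patients, 1:1 allocation, one look at 25, the 50% threshold and the 4 v 2 illustration. Assumed, because the documents give no rates: the complication rates below, independent events, and 13 X-Tack v 12 control at the look and 25 v 25 at the end. With x events on X-Tack (n_x patients) and y on control (n_y patients), two definitions of a signal are used:

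- Example-size: x ≥ 4 and x ≥ 2y.
- Literal threshold: x/n_x > 1.5 × y/n_y, with x > 0 and y = 0 counted as met.

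**Step 1: the single look against the data at patient 50.** The probability at the look is the sum of Bin(x; 13, p_x) × Bin(y; 12, p_y) over the pairs that meet the definition. The last column adds the second-half patients, 12 v 13, and counts trials with no signal at 25 but one at 50. By exact enumeration:

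| X-Tack v control | Definition | At 25 | Absent at 25, present at 50 |
|---|---|---|---|
| 24% v 8% | example-size | 0.361 | 0.396 |
| 16% v 8% | example-size | 0.133 | 0.322 |
| 8% v 8% | example-size | 0.015 | 0.082 |
| 24% v 8% | literal | 0.766 | 0.120 |

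**Step 2: signals early enough to act on.** A signal first present at patient 50 spares nobody. So the cumulative counts are checked at patient 25 and again at each later event, by simulation with alternating allocation:

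- 24% v 8%, example-size: 0.36 at patient 25, 0.77 by patient 45.
- 8% v 8%, example-size: 0.015 at patient 25, 0.11 by patient 50.
- 8% v 8%, literal: 0.35 at patient 25, 0.50 by patient 50.
- 4% v 4%, literal: 0.28 at patient 25, 0.44 by patient 50.

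**Step 3: an excess that arises only in patients 26-50.** Here both arms have 8% up to patient 25, then 24% v 8%. The signal is a rate ratio above 1.5 with at least 4 X-Tack events. One look at 25 shows it in 0.01 of trials, the same as with no excess at all. Adding looks at 30, 35, 40 and 45 gives 0.39.

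**The case against.** A reader might infer that the trial cannot be stopped after patient 25, or that the reviewer is given nothing from then on. The documents support neither. Severe events go to the IRB throughout, and H.1.e makes the IRB a party to the stopping discussion. The monitoring and threshold sentences carry no time limit, and the 25-patient case is only an illustration. On what the reviewer receives later the protocol is silent, which is not an exclusion. This part of the objection stands and limits the point to non-severe events and to the missing tally by arm.

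The gain can also be overstated. Under the literal threshold at 24% v 8%, the share seen only at patient 50 falls from about 40% to 12%. A tripled rate is a favourable scenario: sections G.4 and G.7 expect serious complications to be very rare and the risks of the two systems to be the same. At 8% v 4% the example-size signal is present at patient 25 in under 2% of trials, and only later in about 11%. These are fair limits on the size; they do not supply the missing step.

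More looks mean more false alarms, and under the literal threshold the cost is heavy. That stands and shapes the fix.

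Finally, one midpoint look is a recognisable choice for a 50-patient trial of a cleared device lasting under a year. That is true of the number of formal analyses. It does not explain why later closure complications go to nobody who holds the counts by arm.

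**Conclusion.** The point holds as a gap in the oversight plan. There is one scheduled comparison by arm, a reviewer whose stated role ends with it, and real-time reporting afterwards for severe events only. If monitoring was meant to continue, the protocol does not say who does it, on what data or when.

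The structural finding rests on the text alone. Its size depends on assumed rates and on the definition of a signal: at 24% v 8% with the example-size signal, detection goes from about 36% to about 77% by patient 45, and with lower rates or the literal threshold the gain is smaller. Immediate reporting of severe events mitigates the gap in part. The change is worth making because it is cheap and uses a reviewer already in place.

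H.1.e also contradicts itself on the consequence: the threshold sentence makes stoppage follow, while the illustration makes it a matter for review. This must be reconciled before the criterion is used more often.

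**What to change.** 1. In H.1.e and H.2, state that each severe adverse event, and each perforation or complication related to inadequate closure after the interim analysis, goes to the same independent reviewer with cumulative counts by arm, for review and discussion with the IRB.
2. Reconcile the two statements in H.1.e on whether an excess stops the trial or prompts a review.
3. Have the sponsor define the signal that prompts a review, for example with a minimum event count. Do not re-apply the literal 50% threshold as an automatic stop at each event.

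**Cost.** A few sentences of protocol text, a running tally by arm, and probably a handful of extra messages to the reviewer. The statistical cost is more chance alarms. At an assumed 8% in both arms, an example-size signal rises from about 1.5% at patient 25 to about 11% with event-by-event review to patient 50. If each signal leads to a review, that is acceptable. The literal threshold rises from about 35% to 50%, which is why item 3 belongs with item 1.
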